7.4 Efficacy analysis

All analysis will be conducted in mITT, unless otherwise specified.

7.4.1 Analysis of primary variables

The primary efficacy endpoints for this study are the 240-Week cumulative incidence of newly diagnosed HCC and 240-Week cumulative incidence of disease progression. The newly diagnosed HCC is defined as HCC cases from Week 24 to Week 240. The analysis will be performed in mITT and PP population.

- Nominal cumulative incidence of newly diagnosed HCC at week 240 is defined as the percentage of patient who are newly diagnosed as HCC from Week 24 visit to Week 240 visit in overall patients. Nominal cumulative incidence of HCC will be summarized by frequency, percentage and its 95% two-sided Wald CI. When the value of the newly diagnosed HCC at week 240 is missing due to the epidemic of COVID-19, the missing value may be imputed with the value at the safety follow-up visit. Different missing imputation scenarios will be assessed for the primary analysis and sensitivity analyses, details are provided in below table in which “Y” means the missing value will be imputed with the value at the safety follow-up visit.

Difference between planned Week 240 visit and actual safety follow up visit	Medication taken after previous visit	Primary Endpoints	Sensitivity Analysis 1	Sensitivity Analysis2
<=28 days	Any	Y	Y	Y
>28 days	GSK	Y	N	Y
	Domestic	Y	N	N
	Both GSK & domestic	Y	N	N
Lost to follow up	NA	N	N	N

- Nominal cumulative incidence of disease progression at week 240 is defined as the percentage of patient who have disease progression before Week 240 visit in overall

patients. Nominal cumulative incidence of disease progression will be summarized by frequency, percentage and its 95% two-sided Wald CI. When the value of the disease progression at week 240 is missing due to the epidemic of COVID-19, the missing value will be imputed with the value at the safety follow-up visit. No sensitive analysis is planned.

- Cumulative incidence of newly diagnosed HCC/disease progression at week 240 and its 95% CI will be estimated from the Kaplan–Meier analysis. Time to newly diagnosed HCC/disease progression is defined as the interval between the date of first treatment dose and the analysis date. The rules of analysis date are described in the following table:

Patient's Condition	Status	Analysis date
Diagnosed HCC/disease progression on visit	Event	Date of diagnosis
Reported SAE related with HCC/disease progression between visits	Event	Date of diagnosis
Complete study without HCC/disease progression	Censor	Date of study complete
Lost follow up/ Early withdraws	Censor	Date of last visit with the adequate diagnosis data

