#### **8.3.5.1. Efficacy Analyses**

In this study, data will be summarised as mean, medium, standard deviation, maximum, and minimum for continuous variables, and in tables of frequencies and percentages for categorical variables.

The primary outcomes of this study were the 5-year cumulative incidence rates of HCC, calculated by the Kaplan–Meier method.

Univariate and multivariable analysis by Cox proportional hazards regression model was performed to identify factors associated with HCC. Variables may include serum albumin, total bilirubin, and ALT levels, HBeAg status, serum HBV DNA titer and response to treatment, etc. Effect sizes are expressed as hazard ratios (HRs) and 95% confidence intervals (CIs).

The detail of primary, secondary and other efficacy endpoint analysis will be included in the RAP.

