3.2 Sample size

3.2.1 Sample size Assumptions

Sample sizes are chosen based on feasibility and precision because no hypothesis is tested in this study.

To decide the number of subjects for analysis, some precision calculations have been performed for the primary endpoint HCC incidence. In the retrospective analysis of GS-US-174-0102 and GS-US-174-0103 trials, HCC incidence over 7 years was approximately 4.5% among patients (23% of whom were Asian, 25 of whom were genotype B or C) with cirrhosis at baseline. Accordingly, we hypothesize that the accumulative incidence of HCC at 240 weeks will be 5% in Chinese compensated cirrhotic patients treated with TDF. The precision is calculated by the following:

$$Precision = Z_{1-\alpha/2} \sqrt{\frac{p(1-p)}{N}}$$

where Z is the critical value of normal distribution corresponding to the probability of $1-\alpha/2$ (corresponding to $(1-\alpha)*100\%$ confidence interval), and p is the percentage of patients who were diagnosed HCC during 240 weeks. Precision is half of the width of 95% confidence interval for the

point estimate. A sample size of 158 patients will allow us to estimate the confidence interval of the incidence with a margin of error at 3.4 % (0.016-0.084). Assuming a 15% drop out rate, 186 patients are to be recruited.

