4. ANALYSIS SET

- Modified Intent-to-treat (mITT) Population

The mITT population is defined as all recruited subjects who receive at least one dose of study medication.

- Per Protocol (PP) population

The PP population will consist of subjects in the mITT population who have no major protocol deviations that impact efficacy evaluation.

- Safety Analysis (SA) population

The SA population is defined as all subjects who receive at least one dose of study medication and have at least one post baseline safety assessment.

All efficacy endpoints will be analyzed using the mITT population and PP population will be used for primary endpoints. All safety endpoints will be analyzed using the SA population.

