6. STATISTICAL CONSIDERATIONS

6.1 General rule

All analysis will be conducted using SAS® Version 9.2 or higher (SAS Institute, Cary, NC). For continuous variables, descriptive statistics will be presented as the mean, standard deviation, minimum, median, maximum, and the number of observations, unless otherwise specified. For categorical variables, the number and percentage for each of the categories will be presented. Counts that are zero will be displayed as “0”. Unless otherwise specified, the denominator for all percentages will be based on the number of subjects in the analysis set of that treatment group. Baseline is defined as the last assessment before administration of the study drug.

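### SAP 7.4.1 does not rank its two estimators for each co-primary endpoint, and it ties its Primary Endpoints column to the one that counts event-free drop-outs as never having the event

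*SAP*

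**What the plan says.** SAP 7.4.1 has three bullets.

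- **HCC, nominal rate.** This is the "percentage of patient who are newly diagnosed as HCC from Week 24 visit to Week 240 visit in overall patients". On the interval: "Nominal cumulative incidence of HCC will be summarized by frequency, percentage and its 95% two-sided Wald CI". The COVID-19 imputation table sits inside this bullet. It has one column for the primary endpoints and two for sensitivity analyses, and subjects lost to follow-up get no imputed value in any column.
- **Disease progression, nominal rate.** This is the "percentage of patient who have disease progression before Week 240 visit in overall" patients, again with a Wald interval. No sensitivity analysis is planned.
- **Both endpoints, Kaplan-Meier.** The Week 240 estimate has a 95% CI. Lost or withdrawn subjects are censored at the last visit with adequate diagnostic data.

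The nominal denominator follows from two other sections. SAP 6.1: "the denominator for all percentages will be based on the number of subjects in the analysis set of that treatment group". SAP 4: "The mITT population is defined as all recruited subjects who receive at least one dose of study medication". The primary analysis is repeated in the per-protocol set.

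The SAP does not say which estimator is primary. Protocol 8.3.5.1 does so for HCC: "The primary outcomes of this study were the 5-year cumulative incidence rates of HCC", by Kaplan-Meier. It names no method for progression. Protocol 8.2.1 (last observation carried forward) and 8.3.5 (last available visit for non-completers) can be read differently.

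**The concern.** This is a single-arm study with no hypothesis test, so the two Week 240 rates and their intervals are the result. Under the nominal rate, a subject who leaves without a recorded event stays in the denominator as event-free. That includes anyone who leaves before Week 24, who cannot contribute an HCC event because only cases from Week 24 count. It also includes, for HCC, a subject who leaves after a progression event other than HCC. The rate is therefore pulled down, and its interval treats follow-up that was not observed as if it had been.

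Without a ranking, the report will carry two Week 240 answers per endpoint, and the lower one is the more favourable to the drug. The HCC sensitivity analyses do not help. Under the SAP 6.1 denominator, a subject whose safety-visit value is not used remains as a non-event. Sensitivity Analyses 1 and 2 can then only equal or lower the primary nominal rate, so they cannot reveal understatement.

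**Working it through.** **Plan's own figures.** Inputs from SAP 3.2.1: p = 5%, half-width e = 3.4 points, 95% confidence (z = 1.96), and "Assuming a 15% drop out rate, 186 patients are to be recruited".

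- N = p(1 − p)(z/e)² = 0.05 × 0.95 × (1.96/0.034)² = 157.8, so 158.
- 158/(1 − 0.15) = 185.9, so 186.

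Both reproduce. The planned precision thus rests on 158 evaluable subjects, whereas the nominal rate divides by all treated subjects, 186 if all are dosed.

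**Expected nominal rate.** Assumptions: constant hazard, drop-out unrelated to risk, true 240-week risk F, drop-out d = 15%. The Week 24 start of HCC counting is ignored. With λ = −ln(1 − F) and drop-out spread evenly over follow-up, the mean risk observed in drop-outs is 1 − F/λ, and

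nominal rate = (1 − d)F + d(1 − F/λ).

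- F = 5%: λ = 0.0513, so 0.85 × 5% + 0.15 × 2.52% = 4.63%. Shortfall about 0.4 points, or 7% of the true rate.
- F = 10% (assumed): 0.85 × 10% + 0.15 × 5.09% = 9.26%.
- F = 20% (assumed): 0.85 × 20% + 0.15 × 10.37% = 18.56%.

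Timing sets the range for HCC. If all drop-out is at the very start, the rate is 0.85 × 5% = 4.25%; if all is at the end, 5%.

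The documents give no progression rate, so 10% to 20% is an assumption.

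**Intervals and coverage.** 3,000 simulated trials per row, N = 186, 15% drop-out. Kaplan-Meier uses plain Greenwood intervals, since the SAP does not specify the type. Early means within the first tenth of follow-up (24 weeks). Values are percentages; half-widths are in points.

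| True risk | Drop-out | Nominal (half-width) | Kaplan-Meier (half-width) | Coverage, nominal / KM |
|---|---|---|---|---|
| 5 | even | 4.63 (2.97) | 5.01 (3.21) | 93.6 / 93.2 |
| 5 | early | 4.29 (2.86) | 5.00 (3.33) | 90.5 / 92.3 |
| 10 | even | 9.27 (4.13) | 10.01 (4.46) | 88.8 / 93.5 |
| 10 | early | 8.62 (4.00) | 10.05 (4.63) | 83.1 / 94.0 |
| 20 | even | 18.44 (5.55) | 19.89 (5.96) | 90.1 / 94.4 |
| 20 | early | 17.07 (5.38) | 19.88 (6.17) | 79.3 / 94.3 |

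With no drop-out the two methods coincide. Coverage is then about 95.5% at a 5% risk, 91.8% to 92.8% at 10%, and 94.7% to 94.9% at 20%. Part of the low figure at 10% is therefore the Wald interval itself, not drop-out.

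**Informative drop-out.** If drop-outs carry two or three times the hazard of completers, with even timing and an overall true risk of 5%, the nominal HCC rate is 4.37% or 4.17%. Kaplan-Meier would also be biased low in that case.

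**The case against.** The strongest reply is that the plan already contains the better estimator. The SAP names its primary endpoint as a cumulative incidence. The Kaplan-Meier bullet uses that term without qualification, while the crude rate is labelled nominal. The SAP is to be read with the protocol, which names Kaplan-Meier for HCC. Tables 4.1.1 to 4.1.4 and 4.2.1 to 4.2.4 show both estimators in both populations, so nothing would be hidden. All of this stands. It limits the harm, but it does not supply the missing ranking, and the Primary Endpoints column points to the nominal rate.

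A second reply is that the protocol is not of one mind. Sections 8.2.1 and 8.3.5 handle non-completers by the last available visit, which can be read as support for the nominal rate, and 8.3.5.1 names Kaplan-Meier for HCC only. This also stands, and it is a reason for the SAP to settle the matter.

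Third, Kaplan-Meier is not neutral. For HCC it censors deaths without HCC, and it censors subjects who leave after another progression event, which may be informative. Moving the COVID-19 scenarios to it would also leave them largely one-directional: discarding a late diagnosis still lowers the estimate, and earlier censoring of a non-event barely moves it.

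Three stronger readings are tempting, and the documents do not support them.

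- A reader might infer that every drop-out counts as event-free. Subjects who withdraw after an event keep it for that endpoint, and Week 240 values missed because of COVID-19 can be filled from the safety visit.
- A reader might infer that all estimates of both co-primary rates are biased in this way. The Kaplan-Meier estimates in the same section censor drop-outs.
- A reader might compare a half-width of 3.0 with the planned 3.4 points. The 3.4 is a planning figure for 158 subjects; the like-for-like gap on 186 is 3.0 against 3.2.

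**Conclusion.** The concern holds in limited form. SAP 7.4.1 leaves two estimators unranked for each co-primary endpoint and attaches its primary-endpoint imputation rule and HCC sensitivity analyses to the one that is biased low.

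For HCC the effect is small at the plan's own inputs: about 0.4 points with even drop-out (0 to 0.75 by timing), inside an interval of about ±3 points, with nearly equal coverage for the two methods. For progression it matters more: about 0.7 to 1.5 points low and 89-90% coverage against 94%, given an assumed 10% to 20% risk and even drop-out. These sizes rest on a constant hazard, 15% drop-out and non-informative censoring. The direction of the bias in the nominal rate needs only that some drop-outs without a recorded event would have had one by Week 240.

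The sample size is not affected.

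**What to change.** - State in SAP 7.4.1 that the Kaplan-Meier Week 240 estimate with its 95% CI is primary for HCC, as in Protocol 8.3.5.1, and for disease progression for consistency.
- Keep the nominal percentage as a descriptive row, labelled to show that withdrawals without a recorded event are counted as event-free.
- If the COVID-19 scenarios are moved to Kaplan-Meier, state how a diagnosis or a negative result at a late safety visit is dated for the Week 240 estimate. Events are dated at diagnosis, so without such a rule a diagnosis made after Week 240 would not enter that estimate. Where the safety visit is not used, censor at the last adequate visit.
- Add a cumulative incidence function with death as a competing event, as a check on the HCC estimate.

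The cost is SAP wording and one added check. Kaplan-Meier Tables 4.1.3, 4.1.4, 4.2.3 and 4.2.4 are already listed, and no new data or subjects are needed. The headline rates will be slightly higher and their intervals slightly wider, and the assumption of non-informative censoring should be stated with them.

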## Study Endpoints/Assessments

### Primary Endpoint

- Incidence of hepatocellular carcinoma at Week 240.
- Incidence of disease progression at Week 240, defined as the first occurrence of any one of the following criteria:
  - An increase in Childs-Pugh score (as defined in Appendix 1) of 2 or more points from baseline. an increase in Childs-Pugh score of 2 or more points, solely based on laboratory parameters (i.e. bilirubin, prothrombin time and/or albumin), confirmed between two consecutive visits at least one month apart;
  - spontaneous bacterial peritonitis (with proven sepsis);
  - renal insufficiency defined as a decrease in creatinine clearance rate to  $\leq 50$  mL/minute confirmed on two occasions at least one week apart (calculated from serum creatinine concentration, see section 11.2 Appendix 2);
  - bleeding gastric/oesophageal varices;
  - hepatocellular carcinoma;
  - liver-related death

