5. STUDY ENDPOINTS

5.1 Primary endpoint

- The cumulative incidence of newly diagnosed hepatocellular carcinoma (HCC) at Week 240, the subject must meet one of the following criteria:
 - Without HCC before Week 24
 - A histological diagnosis of HCC (i.e. by biopsy or at post-mortem);
 - In patients with nodules > 2 cm, identification of typical HCC characteristics (hypervascular in the arterial phase with washout in the portal venous or delayed phases) by 4-phase multidetector CT scan or dynamic contrast-enhanced MRI;
 - In patients with nodules > 1 cm, identification of typical HCC characteristics by both techniques (4-phase multidetector CT and dynamic contrast-enhanced MRI).
- The cumulative incidence of disease progression at Week 240, defined as the first occurrence of any one of the following criteria:
 - An increase in Childs-Pugh score (as defined in Appendix 2) of 2 or more points from baseline;
 - An increase in Childs-Pugh score of 2 or more points, solely based on laboratory parameters (i.e. bilirubin, prothrombin time and/or albumin), confirmed between two consecutive visits at least one month apart;
 - Spontaneous bacterial peritonitis (with proven sepsis);
 - Renal insufficiency defined as a decrease in creatinine clearance to ≤ 50 mL/minute confirmed on two occasions at least one week apart (calculated from serum creatinine concentration);
 - Bleeding gastric/oesophageal varices;
 - Hepatocellular carcinoma;
 - Liver-related death.

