6.2 Data handling

Missing data can have an impact upon the interpretation of the trial data. In general, values for missing data will not be imputed unless otherwise specified. For baseline value, if it is missing at baseline visit, then the latest non-missing value of screening will be used to replace.

All serum HBV DNA results below the lower limit of detection (<20 IU/mL) or results of “not detected” will be analyzed as being the value of the lower limit of quantification, which is 20 IU/mL. For patients whose week 240 visits were influenced by COVID-19, a safety follow-up were added for these subjects. The missing week 240 will be imputed from safety follow-up visit in the analysis of primary endpoints. Please refer to section 7.4 for details.

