7.4.2 Analysis of secondary variables

7.4.2.1 Nominal Cumulative Incidence and Nominal Incidence by visit

As defined in previous, the nominal cumulative incidence of newly diagnosed HCC and the nominal cumulative incidence of disease progression at Week 48, Week 96, Week 144, and Week 192 will be summarized by frequency, percentage and its 95% two-sided Wald CI. The analysis will be performed in mITT. Figures of nominal cumulative incidence of HCC/disease progress by each visit will be product respectively.

The nominal incidence at visit is defined as the percentage of subjects who had event during the previous visit to the current visit. The nominal incidence of newly diagnosed HCC and disease progression at each visit from Week 36 (Week 36, 48, 60, 72, 84, 96, 108, 120, 132, 144, 156, 168,

180, 192, 204, 216 and 240) will be summarized by frequency, percentage and its 95% two-sided Wald CI.

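### SAP 7.4.1 ends the nominal progression rate before the Week 240 visit, contradicting the rest of the plan and the adjacent HCC rate; the effect on the crude rate is small

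*SAP*

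**What the plan says.** SAP 7.4.1 reports each co-primary endpoint in two ways: a nominal (crude) percentage with a Wald interval, and a Kaplan–Meier estimate. The two nominal definitions stand in adjacent bullets.

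- HCC: "the percentage of patient who are newly diagnosed as HCC from Week 24 visit to Week 240 visit in overall patients".
- Disease progression: "the percentage of patient who have disease progression before Week 240 visit in overall" patients.

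The progression bullet then adds: "When the value of the disease progression at week 240 is missing due to the epidemic of COVID-19, the missing value will be imputed" from the safety follow-up visit. It states that no sensitivity analysis is planned for this endpoint.

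Elsewhere the endpoint is placed at Week 240, with no earlier cut-off:

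- SAP 5.1: "The cumulative incidence of disease progression at Week 240, defined as the first occurrence of any one of the following criteria". HCC is one of the listed criteria.
- Protocol, Primary Endpoint: "Incidence of disease progression at Week 240, defined as the first occurrence of any one of the following criteria".
- SAP 6.2, on visits disrupted by COVID-19: "The missing week 240 will be imputed from safety follow-up visit in the analysis of primary endpoints".

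SAP 7.4.2.1 carries the nominal definition to earlier landmarks: "As defined in previous, the nominal cumulative incidence of newly diagnosed HCC and the nominal cumulative incidence of disease progression at Week 48", and likewise at Weeks 96, 144 and 192. The same section defines a by-visit nominal incidence that runs from the previous visit to the current one and includes Week 240 among its visits.

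**The concern.** Week 240 is a full assessment visit. Protocol Table 1 schedules chemistry, prothrombin time and INR, ultrasound and AFP there. These feed several progression criteria: the Child-Pugh laboratory items, creatinine clearance, and the imaging that starts an HCC work-up. A window that closes before that visit leaves out whatever is found at it.

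Two things follow if the sentence is programmed as written. First, the crude progression rate omits findings made at the landmark visit that it is named after. Second, the two co-primary rates stop being nested: an HCC found at Week 240 counts for HCC while the same subject counts as free of progression.

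The sentence is the operative definition for SAP Tables 4.2.1 (mITT) and 4.2.2 (PP). Two programmers could reach different counts, each citing the SAP, and no planned sensitivity analysis for progression would reveal the difference.

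**Working it through.** **The plan's own figures.** The precision calculation in SAP 3.2.1 concerns HCC and is not touched by this point. N = p(1−p)(z/e)² with p = 0.05, z = 1.96, e = 0.034 gives 157.8, so 158. The Wald interval at 158 is 0.016–0.084. Allowing for 15% dropout, 158/0.85 = 185.9, so 186. All reproduce.

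**Which places include the Week 240 result?**

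| Place | Treatment of Week 240 progression |
|---|---|
| SAP 7.4.1, nominal definition | Excluded if read literally |
| SAP 7.4.1, same bullet, COVID-19 rule | Value needed, and imputed if missed |
| SAP 6.2 | Missing Week 240 imputed for the primary endpoints |
| SAP 5.1 and protocol, Primary Endpoint | At Week 240 |
| SAP 7.4.2.1, by-visit nominal incidence | Included as the last visit listed |
| SAP 7.4.1, Kaplan–Meier rules | An event diagnosed on a visit counts, the same for both endpoints |

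One phrase stands against all the others.

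**Size at Week 240 if the phrase is applied.** Inputs: 186 subjects, and 12-weekly visits, so 240/12 = 20 scheduled visits. The progression rate is not in the documents; 10–20% over 240 weeks is an assumption. All events are taken as found at visits.

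- Even spread, share lost 1/20. At 10%: 186 × 0.10/20 = 0.93 events (0.5 points). At 20%: 186 × 0.20/20 = 1.86 events (1.0 point).
- Constant hazard, rate by Week 228 = 1 − (1−P)^(228/240). At P = 10%: 9.5%, a loss of 0.88 events. At P = 20%: 19.1%, a loss of 1.67 events.
- For scale, the Wald half-width at N = 186 is 1.96 × √(P(1−P)/186): 4.3 points at 10% and 5.7 points at 20%. At 10% the interval is 5.7–14.3% with Week 240 included and 5.3–13.7% without it (constant hazard).

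**Chance of the HCC anomaly.** Take the plan's 5% HCC incidence, assumed to accrue at a constant hazard over Weeks 24–240 (216 weeks). The probability of falling in the last 12 weeks is 0.95^(204/216) − 0.95 = 0.0027. Expected cases are 0.50 of 186 (0.43 of 158). The chance of at least one is 1 − (1 − 0.0027)^N, about 40% with 186 and 35% with 158.

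**Earlier landmarks, only if the cut-off is also applied there.** With even spread, the share lost is 12/week: 1/4 at Week 48, 1/8 at Week 96, 1/12 at Week 144 and 1/16 at Week 192. In absolute terms at Week 48, constant hazard gives 1 − (1−P)^(48/240) against 1 − (1−P)^(36/240): 2.1% against 1.6% for P = 10%, and 4.4% against 3.3% for P = 20%.

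**The case against.** The strongest reply is that the sponsor plainly meant to include Week 240. A rule for imputing a missed Week 240 progression value has no purpose unless that value enters the rate, and the endpoint is described as being at Week 240 throughout. This stands. A reader might infer from the definition that Week 240 progression is excluded and that the reported rate is biased down. The documents do not support that: they show a contradiction, most likely a slip for wording such as *by* or *up to*, and do not settle which rule would be programmed.

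A reader might also infer large losses at the earlier landmarks. SAP 7.4.2.1 refers back to the definition but never states the cut-off for those weeks. The one-quarter figure at Week 48 needs the strict reading carried over, every event found at a visit, and an even spread. SAP 7.4.1 separately counts events reported as SAEs between visits, and variceal bleeding, peritonitis and liver-related death need not wait for a visit. One quarter is therefore an upper-end illustration.

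The HCC bullet does not say that its upper bound is inclusive either. That is only its natural reading.

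Finally, the Kaplan–Meier estimate of the same endpoint is correctly defined and unaffected. This limits the consequence but does not repair the nominal definition, which is a stated primary result with its own tables.

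**Conclusion.** The nominal progression definition in SAP 7.4.1 is wrong as written and minor in size. It conflicts with its own bullet, SAP 5.1, 6.2 and 7.4.2.1, and the protocol, and its upper bound differs from that of the adjacent HCC rate. Applied literally, it would omit progression found at the Week 240 visit and let a Week 240 HCC count as HCC but not as progression.

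At assumed progression rates of 10–20% in 186 subjects, about 0.9–1.9 events (0.5–1.0 points) would be lost if events are visit-detected, and fewer if some are reported between visits. That is small beside a half-width of 4.3–5.7 points. A larger proportional loss at earlier landmarks, at most about one quarter at Week 48, arises only if the same cut-off is applied there. The Kaplan–Meier estimates and the sample size do not change.

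**What to change.** In SAP 7.4.1, define the nominal progression window as running from first dose up to and including the Week 240 visit, or the safety follow-up visit that replaces it under the COVID-19 rule. Give the nominal HCC rate the same explicit upper bound. In SAP 7.4.2.1, state that the Week 48, 96, 144 and 192 nominal rates include the landmark visit.

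Naming the replacement visit matters: an inclusive Week 240 bound alone would clash with the imputation sentence in the same bullet. It would also help to state, identically for both endpoints, how a finding first seen at Week 240 but confirmed later is handled. SAP 5.1 requires repeat confirmation for laboratory-only Child-Pugh rises and for creatinine clearance, and a nodule on ultrasound needs CT or MRI. Without a common rule the two rates may still fail to nest.

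The cost is a short wording change and the matching program lines. No design feature, sample size or data collection changes. If the literal rule had been programmed, the reported crude progression rate could rise slightly.
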